- b. **Inadequate responders** will enter Treatment Period 2 and will be randomized (1:1, double-blinded) to secukinumab 300 mg or secukinumab 150 mg very 4 weeks through Week 48. Subjects will know that they are on secukinumab, but will be blinded to dose, as they will not know whether they are receiving 150 mg or 300 mg.
- c. **Nonresponders** will be discontinued from the study at Week 16.

The only condition that will be placed on enrollment targets is that no less than 60% of patients (162 patients) are TNF $\alpha$  inhibitor naive (or, no more than 40% of patients are TNF-IR). In theory the percentage of TNF $\alpha$  inhibitor naive patients could reach 100%, although that is not anticipated.

Patients may discontinue the study at any time. If rescue treatment with prohibited medications occurs, patients will be discontinued from the study and will return for an End of Study Visit. The End of Study Visit will be scheduled approximately four weeks after the last study treatment, and will be performed before any new treatment is initiated. After the End of Study Visit, any SAEs that occur in the following 30 days will be reported.

[figure not shown]

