## 2.2 Analysis sets

The following analysis sets will be used for the statistical reporting and analyses:

**Enrolled Set:** The Enrolled Set consists of all enrolled patients for the initial 16-week, Treatment Period 1.

Note: For safety analyses, the Enrolled Set will consist of enrolled patients for the initial 16-week, Treatment Period 1 who received at least one dose of the open-label treatment, secukinumab 150 mg.

**Responder Set:** The Responder Set consists of all patients who are labeled as responders at the end of Treatment Period 1, and enter Treatment Period 2 receiving blinded secukinumab 150 mg every 4 weeks through Week 48.

**Safety Set:** The Safety Set includes all patients who received at least one dose of study treatment during Treatment Period 2. Patients will be analyzed according to the study treatment received.

**Full Analysis Set:** The Full Analysis Set comprises all patients to whom study treatment has been assigned by randomization. According to the intent-to-treat principle, patients will be analyzed according to the treatment they have been assigned to during the randomization procedure.

**Non-responder Set:** The Non responder Set consists of all patients who are labeled as non-responders at the end of Treatment Period 1 and do not enter Treatment Period 2.

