### **2.5.2 Statistical hypothesis, model, and method of analysis**

Let  $\pi_j$  denote the probability of an ASDAS inactive disease at Week 52 for treatment group  $j$ ,  $j = 1, 2$ , where 1 and 2 correspond to secukinumab 150 mg and secukinumab 300 mg, respectively. Accordingly,  $\pi_j/(1 - \pi_j)$  is the odds for treatment group  $j$ ,  $j = 1, 2$ .

The primary efficacy variable will be analyzed at each time point until Week 52 using a logistic regression model with treatment, TNF-alpha inhibitor status (naive, inadequate responder), and Week 16 body weight as explanatory variables (Stokes, Davis, and Koch, 2012). The odds ratios and 95% confidence intervals for the odds ratios will be reported, based on the fitted model.

Number and percentages for ASDAS inactive disease response will also be reported for each treatment group, by TNF-alpha inhibitor status (naive, inadequate responder) by visit. A line plot for ASDAS inactive disease responders (%) from Week 16 to Week 52 will be presented. A similar line plot will be presented by TNF-alpha inhibitor status.

A line plot for ASDAS inactive disease responders (%) over entire treatment period (from Week 1 to Week 52) will be presented. A similar line plot will be presented by TNF-alpha inhibitor status.

Also, number and percentages for the patients with ASDAS inactive disease response in Treatment Period 1 who entered Treatment Period 2 will be provided based on the below criteria:

- Patients receiving 150mg (open label) (Enrolled Set)
- Patients receiving randomized 300mg and 150mg (Randomized Set)
- Patients who are responders (Responder Set)
- Patients who are nonresponders (Nonresponder Set)

In addition, the above analysis will be done by TNF-alpha inhibitor status and by visit.

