#### Change from Week 16 in total BASDAI

Analysis of change from Week 16 in total BASDAI score will be performed using mixed-effects model repeated measures (MMRM) with treatment, visit, and TNF-alpha inhibitor status (naive, inadequate responder) as factors, Week 16 score and Week 16 weight as covariates, and treatment-by-visit and Week 16-by-visit as interaction terms (Diggle, Heagerty, and Liang KY, 2002). The least-squares (LS) mean difference between secukinumab 150 mg - 300mg (IR) and secukinumab 150 mg - 150mg (IR) will be presented along with the corresponding 95% CI.

Similar analysis will be performed for the subgroups defined by TNF-alpha inhibitor status.

Descriptive summary statistics for change from baseline in Treatment Period 1 and change from Week 16 in Treatment Period 2, for total BASDAI score for each visit will be provided. Similarly, descriptive summary statistics will also be provided by TNF-alpha inhibitor status.

Analysis of change from Week 16 in **ASAS-Health Index** and change from Week 16 in **FACIT-Fatigue** will be similar to analyses as described for change from Week 16 in total BASDAI.

Analysis of **BASDAI50 response**, **ASAS20 response**, **ASAS40 response**, and **ASAS partial remission** will be similar to the analyses as described for reduction in ASDAS  $\geq 1.1$  from Week 16.

Also summary statistics for secondary efficacy variables 1, 2, 4 and 5 for the patients in Treatment Period 1 who entered Treatment Period 2 will be provided based on the below criteria :

- Patients receiving 150mg (open label) (Enrolled Set)
- Patients receiving randomized 300mg and 150mg (Randomized Set)

- Patients who are responders (Responder Set)
- Patients who are nonresponders (Nonresponder Set)

In addition, the above analysis will be done by TNF-alpha inhibitor status and by visit.

As additional analyses, following will be performed on Full Analysis Set:

1. Descriptive summary statistics for change from baseline (Week 0) to all visits in Treatment Period 2 for secondary efficacy variables - total BASDAI, ASAS-Health Index and FACIT-Fatigue, will be provided.
2. Number and percentages of patients for secondary efficacy variables 3 - 6 will also be reported for each treatment group considering baseline (Week 0) to derive the response for Treatment Period 2 and similarly by TNF-alpha inhibitor status only for ASAS20 and ASAS40 response.

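### SAP 2.5.2 and 2.7.2 limit the Treatment Period 1 summaries to patients who go on to Treatment Period 2, yet list the Nonresponder and Enrolled Sets: the first is empty as written, and the second loses about 19% of its patients in 2.7.2 and possibly in 2.5.2

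*SAP*

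**What the plan says.** SAP 2.5.2, after the primary model, adds a descriptive summary of the open-label period: "number and percentages for the patients with ASDAS inactive disease response in Treatment Period 1 who entered Treatment Period 2 will be provided". Four rows follow: open-label 150 mg (Enrolled Set), the randomised patients (Randomized Set), responders (Responder Set) and nonresponders (Nonresponder Set). The results are also wanted by TNF-alpha inhibitor status and by visit.

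SAP 2.7.2, under the BASDAI heading, repeats the list for "summary statistics for secondary efficacy variables 1, 2, 4 and 5 for the patients in Treatment Period 1 who entered Treatment Period 2".

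The set definitions are in SAP 2.2. "The Enrolled Set consists of all enrolled patients for the initial 16-week, Treatment Period 1", with no condition on what happens later. The Nonresponder Set is "all patients who are labeled as non-responders at the end of Treatment Period 1 and do not enter Treatment Period 2". SAP 1.1 agrees: nonresponders "will be discontinued from the study at Week 16".

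Three other places bear on the point:

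- SAP 2.5.3 and 2.7.3 score a patient who discontinues, for whatever reason, as a nonresponder from then on. Neither section limits this to randomised patients.
- SAP 2.7.1 defines variables 1 and 2 (ASDAS reduction of at least 1.1, and change in BASDAI) from Week 16.
- SAP 4 states that the Randomized Set has been deleted, although both lists still use it.

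**The concern.** The lead sentence and the list of sets give two different populations for the same table. For the Nonresponder Set they are mutually exclusive. For the Enrolled Set the lead sentence takes out two groups that belong there by definition: patients who stop during open-label treatment, and patients whose ASDAS did not improve at both Week 12 and Week 16 and who therefore leave.

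These summaries describe the response to the first 16 weeks of 150 mg, which is the background to the escalation question. If the row labelled Enrolled Set holds only patients who moved on, it pools the Responder Set and the randomised patients under a label that promises everyone enrolled. A reader would take its figures as the open-label response of the whole cohort. The early leavers, whom the missing-data rule would count as failures for response variables, would not be counted at all.

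The Nonresponder row matters too. The classification table in SAP 5.6 includes non-responder patterns with ASDAS below 1.3 at one of the two visits (Patients 8 to 13). A by-visit table could show those responses; the entry condition forces the row to be empty or zero.

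**Working it through.** **Plan's own flow (SAP 3, Protocol 9.8).** Inputs: 270 enrolled; 10% discontinue in the open-label period; the rest split into 10% responders, 80% inadequate responders and 10% non-responders.

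- Remaining at Week 16: 270 × 0.90 = 243 (27 early leavers).
- Inadequate responders: 243 × 0.80 = 194.4, which reproduces the plan's figure of about 194 randomised.
- Responders: 243 × 0.10 = 24.3. Non-responders: 243 × 0.10 = 24.3.
- Entering Treatment Period 2: 24.3 + 194.4 = 218.7.
- Removed by the entry condition: 270 − 218.7 = 51.3, or 19% of 270. Of these, 27 are early leavers and 24.3 are non-responders.

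**Nonresponder Set.** By definition 0 of the 24.3 enter Treatment Period 2. If the condition limits the population, the row has n = 0. If it limits only the numerator, the row is 0/24.3 = 0%.

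**2.7.2.** Here the condition is attached to the patients summarised. Variable 2 is a continuous change, and a mean has no separate numerator that the condition could restrict. So it defines the analysed population, and the Enrolled Set row rests on 218.7 of 270 patients.

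**2.5.2.** The sentence describes responding patients and states no denominator. For inactive disease at both Week 12 and Week 16, taking the 24.3 responders as all who meet it:

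- Condition limits the denominator too: 24.3/218.7 = 11.1%.
- Condition limits the numerator only: 24.3/270 = 9.0%.
- Full Enrolled Set with early leavers as nonresponders: 24.3/270 = 9.0%.
- For reference, among those remaining at Week 16: 24.3/243 = 10.0%.

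The gap on the first reading is 2.1 points, a ratio of 270/218.7 = 1.23. On the second it is zero.

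**By-visit rates.** The figures above are for the two-visit classification; the table is wanted by visit, and the documents give no by-visit rates. Assume that 0 to 20% of inadequate responders and 0 to 10% of non-responders are inactive at a given visit. With the denominator restricted, the excess then runs from 1.2 points (11.1% against 9.9%) to 5.5 points (28.9% against 23.4%). With only the numerator restricted, a by-visit rate can instead be too low: if no inadequate responders and 10% of non-responders are inactive, it reads 9.0% against 9.9%.

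**ASAS20 in 2.7.2, illustration only.** With rate r among entrants, rate y among non-responders and early leavers as failures, the all-enrolled rate is (218.7r + 24.3y)/270 = 0.81r + 0.09y, so the restricted rate is higher by 0.19r − 0.09y. Assuming r of 40 to 80% and y of 0 to 20%, that is about 6 to 15 points. Neither rate is in the documents.

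**The case against.** The strongest reply is that this is a drafting slip. The Nonresponder Set was added on purpose, and naming it beside the Enrolled Set suggests that all Treatment Period 1 patients were meant, split by their later path. A programmer faced with an empty row would ask. That is plausible, but the text still has to be corrected, and the correction is the same.

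A reader might infer that both sections inflate the open-label rate by selecting on the outcome. The documents do not support that for 2.5.2, where the condition can be read as qualifying the numerator alone and the named set is all enrolled patients. Nor is the selection wholly on outcome: 27 of the 51.3 removed (53%) are assumed early leavers, and only the other 24.3 are removed for lack of ASDAS improvement.

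Part of the ground is covered elsewhere. SAP 2.1 promises Treatment Period 1 efficacy summaries at each time point without the entry condition, but names no set. SAP 2.7.2 also promises counts by treatment period and BASDAI change from baseline in Treatment Period 1, but opens by placing the secondary analyses on the Full Analysis Set, which holds randomised patients only. Non-responders do have their baseline characteristics and medical history reported (SAP 2.3). None of this settles the denominator of the Enrolled Set row.

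It also stands that the tables are descriptive. Every efficacy objective in SAP 1.2 compares the two randomised doses at Week 52.

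**Conclusion.** The contradiction is certain and occurs twice: the Nonresponder rows are empty or 0% as written. In 2.7.2 the row labelled Enrolled Set omits about 51 of 270 patients (19%), against the set's definition and, for the response variables, against the rule that scores discontinuation as non-response. This would tend to overstate open-label response. The 19% rests on the plan's assumed 10% discontinuation and 10/80/10 split; how far a given rate moves depends on response rates that the documents do not give.

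In 2.5.2 the overstatement is conditional: 11.1% instead of 9.0% for inactive disease at both visits if the denominator is restricted, none if only the numerator is. It would be wrong to infer any effect on the primary result. The Week 52 comparison on the Full Analysis Set, its odds ratio and its confidence intervals do not change. The correction is worth making because it alters reported numbers at almost no cost.

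**What to change.** In SAP 2.5.2 and 2.7.2:

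- Delete the condition on entering Treatment Period 2 from both lead sentences, or confine it to the randomised and Responder rows. If a summary of entrants is wanted, give it a row with its own label.
- For response variables, state that the denominator is every patient in the named set, with those who leave before Week 16 scored as non-response under 2.5.3 and 2.7.3.
- For BASDAI change, report observed values with the number of patients at each visit. The full set cannot serve as denominator for a mean when SAP 4 has dropped both last-observation-carried-forward and multiple imputation for this variable.
- State that variables 1 and 2 are measured from Week 0 in Treatment Period 1; as defined from Week 16, they have no meaning there.
- Replace the deleted Randomized Set by the Full Analysis Set.

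The cost is the rewording of two sentences with their lists, the denominators in the table shells, and a slightly less favourable open-label rate wherever the restricted population would have been used.

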### **2.5.3 Handling of missing values/censoring/discontinuations**

Patients who discontinue prematurely for any reason will be considered nonresponders from the time they discontinued through Week 52. Also, patients who do not have the required data to compute response (ASDAS components) at the specific time point will be classified as nonresponders.

In an additional analysis, missing data for ASDAS inactive disease response will be imputed using multiple imputation. Details for multiple imputation is presented in Appendix [Section 5.4](#).

### **2.5.4 Supportive analyses**

A 95% confidence interval for the difference between the two treatment groups in the proportion of patients who have ASDAS inactive disease response will be calculated using the normal approximation to the binomial distribution for the Full Analysis Set.

The analysis will be performed at each time point in Treatment Period 2.

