## 8. Change from Week 16 in FACIT-Fatigue

### 2.7.2 Statistical hypothesis, model, and method of analysis

Analyses of the secondary efficacy variables will be based on the Full Analysis Set.

#### Reduction in ASDAS $\geq 1.1$ from Week 16

Reduction in ASDAS  $\geq 1.1$  from Week 16 (yes, no) will be analyzed at each time point in Treatment Period 2 until Week 52 using a logistic regression model with treatment, TNF-alpha inhibitor status (naive, inadequate responder), and Week 16 body weight as explanatory variables. The odds ratios and 95% confidence intervals for the odds ratios will be reported, based on the fitted model. Similar analysis will be performed for the subgroups defined by TNF-alpha inhibitor status.

A 95% confidence interval for the difference, at each time point in Treatment Period 2 until Week 52, between the two treatment groups in the proportion of patients who have reduction in ASDAS  $\geq 1.1$  from Week 16 will be calculated using the normal approximation to the binomial distribution for the Full Analysis Set.

Number and percentages of patients with reduction in ASDAS  $\geq 1.1$  from Week 16 will also be reported for each treatment group in each treatment period by visit and similarly by TNF-alpha inhibitor status (naive, inadequate responder).

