## 3 Sample size calculation

The sample size was calculated based on the primary efficacy variable (i.e., ASDAS inactive disease response) at Week 52 for the Full Analysis Set. The expected ASDAS inactive disease response rates for secukinumab 300 mg and 150 mg treatment groups at Week 52 are 20% and 10%, respectively (corresponding to an odds ratio of 2.25), partly based on results from AIN457F2310 (MEASURE 2) study. With approximately 97 patients in each treatment group (total of 194 randomized patients), one will be able to estimate the difference between ASDAS inactive disease response rates of the two treatment groups at Week 52 with a “margin of error” (half-width of confidence interval) of 10% (corresponding to a standard error of 5%) for a two-sided 95% confidence interval (Julious and Patterson, 2004; nQuery Advisor 7.0).

It is expected that the study will need to enroll approximately 270 patients for the 16-week open-label period, to randomize approximately 194 patients who do not achieve ASDAS inactive disease status at Week 16 (inadequate responders). This assumes that 10% of the 270 enrolled patients will discontinue during the 16-week open-label period; among the remaining enrolled patients, it is assumed that approximately 10% will be responders, 80% will be inadequate responders, and 10% will be non-responders.

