### 5.4 Statistical models

#### 5.4.1 Primary analysis

The primary analysis will be performed comparing treatments with respect to the primary efficacy variable in a logistic regression model with treatment, TNF-alpha inhibitor (naive, inadequate responder) and baseline body weight as explanatory variables.

```
Proc logistic data=aaa;  
Class TRT TNF/ param=glm;  
Model AVAL= TRT TNF base_weight;  
Lsmeans TRT / diff cl exp;  
Ods output diffs=lsd_diff;  
Run;
```

Where TRT = treatment group  
TNF = TNF-alpha inhibitor (naive, inadequate responder)  
Base\_weight = baseline body weight

Logistic regression will be applied to response variables at each visit.

In cases where separation is a concern, e.g., 0% response in one treatment group, an exact logistic regression model will be applied.

```
Proc logistic data=aaa exactly;  
Class TRT TNF / param=glm;  
Model AVAL = TRT TNF base_weight;  
Exact TRT / estimate;  
Ods output exactoddsratio=exactoddsratio;  
Run;
```

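### The planned normal-approximation interval for the difference in response rates has no provision for few or no responders; a score-type interval would mend this at almost no cost

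*SAP*

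**What the plan says.** SAP 2.5.4 (Supportive analyses) gives the method for the primary variable: a 95% interval for the between-group difference in the proportion with "ASDAS inactive disease response will be calculated using the normal approximation to the binomial distribution for the Full Analysis Set", at every Treatment Period 2 time point. Protocol 9.4.4 names the same method.

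SAP 2.7.2 repeats it for the proportion whose ASDAS falls by at least 1.1 from "Week 16 will be calculated using the normal approximation to the binomial distribution for the Full Analysis Set". It then carries the same analyses over to BASDAI50, ASAS20, ASAS40 and ASAS partial remission. That makes six binary variables.

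Neither section says what happens when an arm has few or no responders. For the odds ratio the SAP does say. Section 5.4.1 provides: "In cases where separation is a concern, e.g., 0% response in one treatment group, an exact logistic regression model will be applied".

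On rates, SAP 3 says: "The expected ASDAS inactive disease response rates for secukinumab 300 mg and 150 mg treatment groups at Week 52 are 20% and 10%, respectively". No expected rate is given for any other visit or endpoint. The planned precision is a "half-width of confidence interval) of 10% (corresponding to a standard error of 5%) for a two-sided 95% confidence interval".

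**The concern.** The normal-approximation (Wald) interval estimates its variance from the observed proportions. An arm with no responders contributes no variance, and two such arms give an interval of zero width. With few responders the interval is too short.

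This matters because the trial is designed for estimation. The primary objective is worded as a difference in proportions, and the sample size is justified by the half-width of the interval for that difference. The logistic model reports an odds ratio, and the multiple-imputation analysis reports single-arm rates and an odds ratio. The interval in SAP 2.5.4 is therefore the only one on the objective's own scale. At any visit or endpoint with few responders it would claim more precision than the data hold. The SAP already provides for a 0% arm on the odds-ratio scale, but not on this one.

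**Working it through.** **Inputs from the documents.** SAP 3: "With approximately 97 patients in each treatment group (total of 194 randomized patients"; rates of 10% and 20%; two-sided 95% interval; half-width of 10 points. SAP 1.1: inadequate responders "will be randomized (1:1, double-blinded) to secukinumab 300 mg or secukinumab 150 mg".

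**The plan's own figure.** With unpooled variance, n = z²[p₁(1−p₁) + p₂(1−p₂)]/w². The bracket is 0.1×0.9 + 0.2×0.8 = 0.25, so n = 1.96² × 0.25/0.10² = 96.04, rounded up to 97. At n = 97 the standard error is √(0.25/97) = 0.0508 and the half-width is 1.96 × 0.0508 = 0.0995. The stated figure is reproduced, by the same formula that SAP 2.5.4 uses for the analysis.

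**Methods compared.**
- Wald: d ± 1.96 √[p̂₁(1−p̂₁)/n + p̂₂(1−p̂₂)/n], with d = p̂₂ − p̂₁ (300 mg minus 150 mg).
- Newcombe hybrid score, with Wilson limits (lⱼ, uⱼ) for each arm: lower limit d − √[(p̂₂−l₂)² + (u₁−p̂₁)²], upper limit d + √[(u₂−p̂₂)² + (p̂₁−l₁)²].
- Miettinen-Nurminen (MN), for single tables.

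**Single tables, 97 per arm (150 mg against 300 mg), in percentage points.**

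| Responders | Wald | Newcombe | MN |
|---|---|---|---|
| 0 vs 0 | 0 to 0 | −3.8 to 3.8 | −3.8 to 3.8 |
| 0 vs 1 | −1.0 to 3.0 | −2.9 to 5.6 | −2.8 to 5.6 |
| 0 vs 4 | 0.2 to 8.1 | −0.4 to 10.1 | 0.25 to 10.1 |
| 10 vs 19 | −0.7 to 19.2 | −0.9 to 19.4 | −0.8 to 19.6 |

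At 0 against 1 the Wald width is 4.0 points and the Newcombe width 8.5. Near the planning rates (10 against 19) the three methods agree.

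**Exact coverage, 97 per arm.** Coverage is the sum of the two binomial probabilities over all tables whose interval contains the true difference. Only the first row uses rates from the documents; the others are assumed.

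| True rates, 150 vs 300 mg | Wald coverage | Upper limit too low (nominal 2.5%) | Lower limit too high (nominal 2.5%) | Newcombe coverage |
|---|---|---|---|---|
| 10% vs 20% | 94.75% | 2.8% | 2.4% | 95.2% |
| 3% vs 8% | 93.8% | 4.4% | 1.85% | 96.2% |
| 2% vs 5% | 93.8% | 5.1% | 1.1% | 96.75% |
| 1% vs 5% | 92.5% | 6.5% | 1.0% | 97.25% |
| 1% vs 3% | 92.5% | 6.4% | 1.1% | 99.2% |
| 0% vs 2% | 85.6% | 14.1% | 0.3% | 99.9% |

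In the last row the whole upper-side miss comes from the zero-width interval: both arms have no responders with probability 0.98⁹⁷ = 14.1%.

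**False exclusion of zero when the true rates are equal (Wald, 97 per arm).** 5.2% at 10%, 5.4% at 5%, 4.8% at 3%, 3.9% at 2% and 1.3% at 1%. It is barely above nominal at its worst and falls as rates approach zero.

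**Cost at the planning rates.** The mean half-width is 9.87 points for Wald and 10.06 for Newcombe.

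**The case against.** The strongest reply is that this is a supportive analysis, fixed in protocol 9.4.4 and consistent with the sample-size formula, and that it performs properly at the primary time point. The low rates are assumed. Early ASDAS rates need not be near zero, because the table in SAP 5.6 lets patients who are already below 1.3 at Week 12 or Week 16, but not both, enter the randomized group. Nothing in the documents points to sparse counts for ASAS20, ASAS40 or BASDAI50. Newcombe has its own departure from 95%: 99.2% at 1% against 3%.

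Most of this stands, and it sets the priority. It does not close the gap. SAP 2.1.1 makes Week 16 the baseline for Treatment Period 2 analyses, and missing components count as non-response, so low counts at early visits are possible though not shown.

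Four stronger readings are tempting, and the documents do not support them:

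- *The SAP expects arms with 0% response.* Section 5.4.1 names 0% only as an example of when a fallback applies. The stated expectation is 10% and 20% at Week 52, and at a true 10% the chance of 0/97 is 0.004%.
- *The interval will wrongly exclude zero.* The 0 against 4 table excludes zero while Fisher's exact p is 0.12, but MN, a score method, excludes zero there too. The long-run rates above show no material inflation.
- *The difference is the only rate estimate on Wald limits.* In the multiple-imputation analysis of 5.4.1 the usual limits are normal limits on the logit scale. Wilson limits serve only the degenerate cases. The score interval in 5.4.6 is for crude event incidence.
- *Coverage collapses in the TNF-inadequate-responder subgroup.* If the 40% enrolment cap carried over to randomized patients, that would be about 0.40 × 97 = 39 per arm, with Wald coverage of 77.2% at 1% against 3%. But SAP 2.5.4 and 2.7.2 specify the difference interval for the Full Analysis Set. The subgroup sentence in 2.7.2 belongs to the odds-ratio paragraph.

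**Conclusion.** The point holds as a modest gap. The plan's only interval on the scale of its objective has no provision for sparse counts, at any Treatment Period 2 visit, for six binary variables. Week 52 at the planning rates is essentially unaffected (94.75%).

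The loss elsewhere depends on rates the documents do not give. Over the assumed pairs in the coverage table with some response in both arms it is 1.2 to 2.5 points of coverage. It reaches 9.4 points (95 − 85.6) at 0% against 2%. The error is false precision: when 300 mg has the higher rate, the upper limit understates how large its advantage could be. Zero width needs 0% (or 100%) in both arms; 0% in one arm alone gives a positive but short interval. These figures assume 97 per arm and independent binomial counts. The priority is low.

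**What to change.** In SAP 2.5.4 and 2.7.2, replace the normal approximation with one named score-type interval for the difference in proportions, either Newcombe hybrid score or Miettinen-Nurminen. Use it at all visits and for all six binary variables, and list the change in SAP 4. A second Wald interval at Week 52 is unnecessary, since the methods nearly coincide there.

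The cost is a wording change and one procedure option. With Newcombe, the mean half-width at the planning rates rises by 10.06 − 9.87 = 0.19 points, so the sample-size rationale stands. The drawback is that Newcombe is mildly to clearly conservative at very low rates.
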